9.1 Definition of Baseline and Change from Baseline

If not otherwise specified, 'baseline' refers to the last scheduled measurement before administration of study intervention.

However, if a participant is missing the baseline collection, the previous non-missing evaluation could become the baseline value (e.g. from Screening). If no baseline or previous to baseline evaluations exist, then the baseline value will be treated as missing.

Absolute changes from baseline are defined as

$$\text{absolute change} = \text{visit value} - \text{baseline value}$$

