Cocktail (Day 1):	Single oral dose substrate cocktail on Day 1: digoxin (0.25 mg), metformin (10 mg), rosuvastatin (10 mg)
Evobrutinib (Days 4 to 9):	45 mg Evobrutinib multiple doses twice daily on Days 4 to 9
Evobrutinib+Cocktail (Day 10):	45 mg Evobrutinib multiple oral doses twice daily on Days 4 to 12 plus Cocktail on Day 10

The following labels will be used for the study interventions in tables and listings of Part 2, if not stated otherwise:

Sumatriptan (Day 1):	25 mg Sumatriptan single oral dose on Day 1
Evobrutinib (Days 2 to 7):	45 mg Evobrutinib multiple doses twice daily on Days 2 to 7
Evobrutinib+Sumatriptan (Day 8):	45 mg Evobrutinib multiple doses twice daily on Days 2 to 8 plus Sumatriptan on Day 8

Note: The label "Evobrutinib" is applicable to adverse event (AE) tables and listings only.

All tables, listings and figures will be provided by part.

All statistical analyses will be performed using SAS® Software version 9.2 or higher.

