9.2 Study Day / Study Intervention Day

Day 1 is the day of start of study intervention, the day before is Day -1 (no Day 0 is defined). Study day is defined relative to Day 1.

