9.3 Definition of Duration and 'Time Since' Variables

The following definitions and calculations of duration, as applicable, will be applied:

- Duration of adverse event (AE) (in days hh:mm) = end date and time - start date and time of the AE, if missing time for either the beginning or end then = end date - start date + 1; in case of multiple records for the same AE, the duration will be calculated over all these records
- Days hh:mm from dosing (onset post administration) = start date and time of the event - date and time of last dose administration of cocktail, evobrutinib or sumatriptan (calculated for each intervention, for TEAEs), if missing time for either the dosing or event then days hh:mm from dosing = event start date - date of dose administration + 1
- Relative (Rel.) Day in study of AE = start date of the event - date of first admin in period + 1 (for AEs on or after the day of dosing)
- Rel. Day in study of AE = start date of the event - date of first admin (for events before the day of dosing of the study only)

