10.2 Protocol Deviations / Exclusion from Analysis Sets

10.2.1 Important Protocol Deviations

Listings of important protocol deviations will be provided including the date and relative day in relation to dosing in the relevant period. A distinction will be made between important protocol deviations due to COVID-19 versus not due to COVID-19. The respective important protocol deviations will be flagged accordingly.

Important protocol deviations or important events that might have an effect on PK include, but may not be limited to the following:

- Adverse events, diarrhea etc. (these instances will be discussed on a case-by case basis)
- Vomiting after administration following oral dosing (these instances will be discussed in alignment with applicable regulatory guidelines on a case-by case basis)
- Sample processing errors that may lead to inaccurate bioanalytical results
- Inaccurate dosing or dosing errors (e.g. dose administration delayed, dose change or missed doses)
- Pre-dose or trough sample collected after the actual dosing
- Non-compliance with food and drink requirements (e.g. non-fasted, incomplete meal consumption, caffeine intake)
- Concomitant medication, vitamins, dietary or herbal supplements

Should one or more of these events be available at the Data Review Meeting, its implication for PK evaluation will be discussed and agreed amongst relevant study team members (e.g. Sponsor Clinical Pharmacology/Biostatistics/Clinical Pharmacokinetics & Pharmacodynamics team representative). Appropriate action will be taken such as flagging individual values to be excluded from analysis.

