11.3 Other Baseline Characteristics

Other baseline measurements, such as virus screen, alcohol and drugs of abuse screen, pregnancy test in women, nicotine, and alcohol consumption, will be listed.

Baseline characteristics with respect to vital signs, physical examinations, and hematology/biochemistry will be part of Section 15 (Safety Evaluation).

12 Previous or Concomitant Therapies/Procedures

Medications will be presented for the Safety Analysis Set.

Previous medications are defined as any medication discontinued prior to the administration of study intervention. Concomitant medications are defined as any medication taken during the course of the study, with a starting date greater than or equal to the administration of study intervention, or with a starting date prior to the administration of study intervention and ongoing at the time of the administration of study intervention.

The World Health Organization Drug dictionary (WHO-DD), most current version at time of database lock, will be used for coding of prior and concomitant medications and they will be described using Preferred Term (PT) as applicable.

Previous and concomitant medications will be listed. Concomitant procedures, if any, will also be listed.

13 Study Intervention: Compliance and Exposure

The dosing of each participant is monitored by the study nurse or investigator. A listing of date and time of each drug administration and each blood sampling, including time deviations as well as measured plasma concentrations, will be provided sorted by participant. Information on meal intake will be listed by participant, if provided.

14 Efficacy Analyses

Not applicable.

15 Safety Analyses

This section includes specifications for summarizing safety endpoints that are common across clinical studies such as adverse events, laboratory tests and vital signs.

All safety analyses will be performed for the Safety Analysis Set and will be presented by part, study intervention and nominal timepoint, as appropriate.

Safety analyses will be done according to the as-treated principle.

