15.1 Adverse Events

All AEs recorded during the course of the study will be coded with the MedDRA, latest version at time of data base lock, and assigned to a SOC and a PT.

Treatment-emergent AEs (TEAEs) are those events with onset dates on or after the first administration of study intervention on Day 1. Any AE occurring before the administration of study intervention on Day 1 and resolved before administration of study intervention or not worsening after administration of study intervention in intervention on Day 1 will be included in the AE listings but will not be included in the summary tables (unless otherwise stated). These will be referred to as “pre-treatment” AEs. An AE occurring after administration of any study intervention will be counted towards the last intervention received before the onset, even if the event is not resolved at the beginning of the following intervention. An AE that worsens after a later intervention period will be counted towards both study interventions.

In case AE-related dates are partial, the available information will be used in a conservative approach to determine whether the AE is treatment-emergent.

All analyses described in Section 15.1 will be based on TEAEs if not otherwise specified. The AE listings will include all AEs (whether treatment-emergent or not). AEs outside the on-treatment period will be flagged in the listings.

Unless otherwise specified, TEAEs will be summarized, by number and percentage of participants with the TEAE in the category of interest, as well as the number of events, in total and by study intervention group, primary SOC and PT in alphabetical order for SOC and decreasing overall frequency for PT.

Each participant will be counted only once within each SOC or PT.

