15.3 Clinical Laboratory Evaluation

Listings and summary statistics at each assessment time will be presented using the Système International (SI) units. Normal ranges will be provided by the laboratory department, and out of range flags will be calculated based on the normal ranges. Laboratory data not transferred from the central laboratory in SI units will be converted to SI units before processing. Both original units and SI units will be provided in the SDTM domain.

Safety laboratory parameters are separated into:

- Hematology (including coagulation)
- Biochemistry
- Urinalysis
- Other tests

Hematology, biochemistry, and coagulation will be summarized by study intervention and time point using descriptive statistics for baseline (see definition in Section 9), each evaluation during the study, and change from baseline to each evaluation.

Listings of abnormal test results (low and high) will also be provided.

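### Does the SAP's baseline definition hide evobrutinib effects because it does not name the first dose?

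*SAP*

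**What the plan says.** SAP 9.1 states that baseline, unless specified otherwise, "refers to the last scheduled measurement before administration of study intervention". If that value is missing, the preceding available value may stand in, with Screening given as the example.

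The safety sections refer back to this rule. SAP 15.3 states: "Hematology, biochemistry, and coagulation will be summarized by study intervention and time point using descriptive statistics for baseline". SAP 15.4 and 15.5 use the same form for vital signs and ECG, and all three also ask for change from baseline at each evaluation.

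SAP Section 9 gives three intervention labels per part: substrate alone, evobrutinib alone and the combination. It notes that the evobrutinib-alone label "is applicable to adverse event (AE) tables and listings only".

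The adverse event rule is tied to a dose: SAP 15.1 counts events with onset "on or after the first administration of study intervention on Day 1". Protocol 9.4.2 plans changes from baseline for these safety endpoints and does not define baseline.

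**The concern.** With three interventions per part and tables split by intervention, a programmer might take the predose value of each intervention as its own baseline. Period language elsewhere in the SAP could encourage this: SAP 9.3 uses "date of first admin in period + 1" in an adverse event day formula, and SAP 10.2.1 lists deviations by "relative day in relation to dosing in the relevant period". Neither document defines a period for this single-sequence design.

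On that reading the combination baseline is taken while the participant is already on evobrutinib. There is no placebo arm, no evobrutinib-alone row outside adverse event outputs, and no ECG or vital-sign assessment scheduled between Day 1 and the combination day. No ECG or vital-sign change value would then compare evobrutinib with a drug-free state. The same rule covers laboratory changes, including transaminases, whose elevation Protocol 2.3.1 lists as an identified risk of evobrutinib.

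**Working it through.** **Dose count.** Protocol 6.1 gives evobrutinib twice daily, 12 hours apart, on Days 4 to 12 (Part 1) and Days 2 to 8 (Part 2). The second substrate dose is on Day 10 or Day 8. Protocol 4.2 states a lead-in of 6 days, which reproduces: 10 − 4 = 6 and 8 − 2 = 6.

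- Doses before the combination-day predose value: 6 × 2 = 12 in each part.
- Total doses: (12 − 4 + 1) × 2 = 18 in Part 1; (8 − 2 + 1) × 2 = 14 in Part 2.
- Share given before that value: 12/18 = 67%; 12/14 = 86%.

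**Difference between the readings.** Let x be a later value, D1 the Day 1 predose value and Dc the Day 10 or Day 8 predose value. Then (x − D1) − (x − Dc) = Dc − D1. For illustration, assume an acute effect of 3 units at 4 hours and a persistent shift of 0, 2, 5 or 10 units. The 4-hour change is 3, 5, 8 or 13 from Day 1, and 3 in every case from the combination-day predose value.

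**Time points affected.** After the first dose, Part 1 has six ECG and vital-sign time points: Day 1 at 4 and 6 hours; Day 10 predose, 4 and 6 hours; and Day 13. Four of these depend on the reading. Part 2 has two, Day 8 predose and Day 9, and both depend on it. The Part 2 days and the Day 13 mark are read from column alignment in the schedule (Protocol 1.3), which is not fully clear. Day 13 and Day 9 count only if they carry the combination label, which the SAP does not state.

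**What would be subtracted.** Only what persists at predose, about 12 hours after dose 12. Protocol 2.2 gives a half-life of about 2 hours (1.8 to 2.6). The fraction of concentration left is 0.5^(12/t½): 0.98% at 1.8 h, 1.6% at 2.0 h and 4.1% at 2.6 h. Acute effects of the Day 10 dose stay in the 4- and 6-hour changes.

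**Which reading the text supports.**

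- The Screening fallback in SAP 9.1 fits a baseline before dosing on Day 1. For laboratory tests, sampled at Screening and Day -1, it fits exactly. For a Day 10 or Day 8 baseline, the preceding ECG or vital-sign value would normally be from Day 1.
- SAP 9.2 anchors time once for the whole study: "Day 1 is the day of start of study intervention".
- SAP Section 12 defines previous medication as "any medication discontinued prior to the administration of study intervention". It too omits first, yet can only sensibly mean the start of dosing. SAP 15.1 does the same when it describes pre-treatment events.
- SAP 11.3 places the vital-sign and laboratory baseline characteristics of participants in Section 15, so the baseline used there describes participants at entry.
- Protocol 8.2.2 limits height to baseline, treating baseline as one occasion.
- Protocol 9.4.2 runs the laboratory, ECG and vital-sign endpoints from the first dose to the end of participation, and SAP Section 7 declares no departure from the protocol's analyses.
- The period wording in SAP 9.3 and 10.2.1 governs adverse event day and deviation listings. It does not govern baseline.
- Splitting tables by intervention arranges rows and is compatible with one common baseline.

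**The case for a change.** The strongest case for a change is that the rule names no dose, the SAP names the first dose where it defines treatment-emergent events, and one added word before database lock would remove all doubt. The fallback could also mix baselines on the per-intervention reading: if a Part 1 Day 10 predose ECG were missing, the preceding value would be the Day 1 6-hour one, taken after the cocktail but before evobrutinib. Low plasma concentration at predose does not rule out a lasting effect either, since evobrutinib is an irreversible inhibitor (Protocol 2.2).

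The ambiguity stands, and so do the dose count and the algebra. The consequence is much weaker. SAP 15.3 to 15.5 summarise the values at baseline and at each evaluation, so with complete data the mean shift is the difference between two displayed predose means, and individual values are listed. A same-day predose baseline is itself a defensible convention for isolating the acute effect of a dose, and SAP Section 9 makes combination versus substrate alone the default comparison.

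The laboratory argument adds little. If the combination-day sample is predose (its clock time is not stated), the follow-up change covers 6 of 18 doses (33%) or 2 of 14 (14%). Treating these as the share of an effect that would be reported assumes linear growth with dose. Without that assumption the share runs from 0% to 100%. Protocol 2.3.1 adds that the transaminase elevations were not seen in healthy participants after one dose, or in participants treated briefly. The transaminase and bilirubin thresholds for events of special interest (Protocol 8.3.7) and the out-of-range flags (SAP 15.3) use reference limits, which do not depend on baseline.

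**Conclusion.** No change to the plan follows. This is a missing word that the surrounding text supplies: one baseline before the first dose on Day 1, common to all intervention labels. On that reading, naming the first dose would alter no result.

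On the other reading, combination-label ECG and vital-sign changes would move by the combination-day predose value minus the Day 1 predose value. That removes only effects lasting to predose, and the displayed absolute values show the shift. Saying that every combination change value is affected further assumes that the follow-up visit carries the combination label and that no predose value is missing. The outputs concerned are descriptive secondary safety tables; the primary AUC and Cmax comparisons do not use this baseline.

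The conclusion rests on analysts following the Screening fallback and the first-dose window of the protocol endpoints, which is the ordinary course.

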9.2 Study Day / Study Intervention Day

Day 1 is the day of start of study intervention, the day before is Day -1 (no Day 0 is defined). Study day is defined relative to Day 1.

9.3 Definition of Duration and 'Time Since' Variables

The following definitions and calculations of duration, as applicable, will be applied:

- Duration of adverse event (AE) (in days hh:mm) = end date and time - start date and time of the AE, if missing time for either the beginning or end then = end date - start date + 1; in case of multiple records for the same AE, the duration will be calculated over all these records
- Days hh:mm from dosing (onset post administration) = start date and time of the event - date and time of last dose administration of cocktail, evobrutinib or sumatriptan (calculated for each intervention, for TEAEs), if missing time for either the dosing or event then days hh:mm from dosing = event start date - date of dose administration + 1
- Relative (Rel.) Day in study of AE = start date of the event - date of first admin in period + 1 (for AEs on or after the day of dosing)
- Rel. Day in study of AE = start date of the event - date of first admin (for events before the day of dosing of the study only)

9.4 Imputation of Missing Data

In this Phase I PK study, missing observations will be assumed to be missing completely at random (MCAR). No action will be taken to handle missing data. A participant who withdraws prior to the last planned observation in a study period will be included in the analyses up to the time of discontinuation.

10 Study Participants

The subsections in this section include specifications for reporting participant disposition and study intervention/study discontinuations. Additionally, procedures for reporting protocol deviations are provided.

10.1 Disposition of Participants and Discontinuations

The following will be presented in a summary table:

- Total number of participants screened (i.e., participants who gave informed consent)
- Number of screened participants who discontinued from the trial prior to first dosing overall and grouped by the main reason for discontinuation:
 - Participant did not meet all eligibility criteria
 - Withdrew consent
 - Other (COVID-19-related and COVID-19-non-related)
- Number of treated participants
- Number and percentage of treated participants who completed study
- Number and percentage of treated participants who discontinued the study or study intervention, with the primary reason of discontinuation:
 - Adverse event
 - Lost to follow-up
 - Protocol non-compliance
 - Death
 - Withdrew consent
 - Other (COVID-19-related and COVID-19-non-related)

The number and percentage of participants will be presented by part, group of study intervention and total, where applicable. Percentages will be presented with respect to the number of treated participants, where applicable.

A listing of discontinued participants will be provided.

A listing of participants affected by the COVID-19 related study disruption by unique participant identifier will also be provided.

10.2 Protocol Deviations / Exclusion from Analysis Sets

10.2.1 Important Protocol Deviations

Listings of important protocol deviations will be provided including the date and relative day in relation to dosing in the relevant period. A distinction will be made between important protocol deviations due to COVID-19 versus not due to COVID-19. The respective important protocol deviations will be flagged accordingly.

Important protocol deviations or important events that might have an effect on PK include, but may not be limited to the following:

- Adverse events, diarrhea etc. (these instances will be discussed on a case-by case basis)
- Vomiting after administration following oral dosing (these instances will be discussed in alignment with applicable regulatory guidelines on a case-by case basis)
- Sample processing errors that may lead to inaccurate bioanalytical results
- Inaccurate dosing or dosing errors (e.g. dose administration delayed, dose change or missed doses)
- Pre-dose or trough sample collected after the actual dosing
- Non-compliance with food and drink requirements (e.g. non-fasted, incomplete meal consumption, caffeine intake)
- Concomitant medication, vitamins, dietary or herbal supplements

Should one or more of these events be available at the Data Review Meeting, its implication for PK evaluation will be discussed and agreed amongst relevant study team members (e.g. Sponsor Clinical Pharmacology/Biostatistics/Clinical Pharmacokinetics & Pharmacodynamics team representative). Appropriate action will be taken such as flagging individual values to be excluded from analysis.

10.2.2 Reasons Leading to the Exclusion from an Analysis Set

If participants are excluded from the PK Analysis Set, the reasons for exclusion will be listed.

Reasons for excluding individual PK concentrations will also be listed separately and flagged in the main listing.

11 Demographics and Other Baseline Characteristics

Demographics and baseline characteristics will be presented for the SAF.

11.1 Demographics

Descriptive statistics will be presented for age, height, weight, and body mass index (BMI). Frequency counts and percentages will be presented for sex, race, and ethnicity. The summary will be performed overall by part.

BMI (kg/m²) will be derived (i.e., not taken directly from the database) according to the following formula:

$$\text{BMI [kg/m}^2\text{]} = \frac{\text{weight [kg]}}{\text{height[cm}^2\text{]}} \times 10000$$

11.2 Medical History

Medical history will be coded using the Medical Dictionary for Regulatory Activities (MedDRA), most current version at time of data base lock, and listed.

The medical history will be listed by participant including preferred term (PT) as event category and system organ class (SOC) body term as Body System category.

11.3 Other Baseline Characteristics

Other baseline measurements, such as virus screen, alcohol and drugs of abuse screen, pregnancy test in women, nicotine, and alcohol consumption, will be listed.

Baseline characteristics with respect to vital signs, physical examinations, and hematology/biochemistry will be part of Section 15 (Safety Evaluation).

12 Previous or Concomitant Therapies/Procedures

Medications will be presented for the Safety Analysis Set.

Previous medications are defined as any medication discontinued prior to the administration of study intervention. Concomitant medications are defined as any medication taken during the course of the study, with a starting date greater than or equal to the administration of study intervention, or with a starting date prior to the administration of study intervention and ongoing at the time of the administration of study intervention.

The World Health Organization Drug dictionary (WHO-DD), most current version at time of database lock, will be used for coding of prior and concomitant medications and they will be described using Preferred Term (PT) as applicable.

Previous and concomitant medications will be listed. Concomitant procedures, if any, will also be listed.

13 Study Intervention: Compliance and Exposure

The dosing of each participant is monitored by the study nurse or investigator. A listing of date and time of each drug administration and each blood sampling, including time deviations as well as measured plasma concentrations, will be provided sorted by participant. Information on meal intake will be listed by participant, if provided.

14 Efficacy Analyses

Not applicable.

15 Safety Analyses

This section includes specifications for summarizing safety endpoints that are common across clinical studies such as adverse events, laboratory tests and vital signs.

All safety analyses will be performed for the Safety Analysis Set and will be presented by part, study intervention and nominal timepoint, as appropriate.

Safety analyses will be done according to the as-treated principle.

